6.1.5. Problem Behaviors Assessment-Short Form

Because of the prominence of psychiatric symptoms in HD, it is recommended that the PBA-s form be used in all HD studies with any need for behavioral assessment as a comprehensive screen for the most common psychiatric symptoms in HD (Craufurd et al 2001; Kingma et al 2008). The PBA-s also includes questions concerning suicidal behavior, a particular concern in HD. The PBA-s is based on the same set of core behavioral symptoms as the UHDRS Behavioral questions, which were used previously as the global psychiatric measure in most HD studies. The PBA-s has more detailed questions and more specific guidance on administration and scoring.

The PBA-s is a brief semi-structured interview covering the most common behavioral and psychiatric manifestations of HD. The interview is not restricted to a single construct, but rather covers several broad symptom domains relevant to HD, comprising 11 items: low mood, suicidal ideation, anxiety, irritability, anger/aggressive behavior, loss of motivation, perseverative thinking or behavior, obsessive-compulsive behaviors, paranoid thinking, hallucinations, behavior suggestive of disorientation. Each symptom is rated for severity on a 5-point scale according to detailed scoring criteria which roughly correspond to the following: 0 = “not at all”; 1 = trivial; 2 = mild; 3 = moderate (disrupting everyday activities) and 4 = severe or intolerable. Each symptom is also scored for frequency on a 5-point scale as follows: 0 = symptom absent; 1 = less than once weekly; 2 = at least once a week; 3 = most days (up to and including some part of every day); and 4 = all day, every day. Severity and frequency scores are multiplied to produce an overall ‘PBA score’ for each symptom.

Only the abbreviated PBA-s (i.e. items of the PBA-s relevant to suicidality [depressed mood, suicidal ideation, anxiety, irritability, loss of motivation, obsessive-compulsive behaviors]) will be collected during the additional safety TC. If the patient has a positive score 1 and 2 on the suicidal ideation item or depressed mood item of the PBA-s, the patient will be monitored more closely and treated according to the investigator's medical judgment. Patients with C-SSRS or PBA-s suicidality scores 1 and 2 may be handled by study investigator/neurologist with a consultancy with psychiatrists where necessary per investigator’s medical judgement.

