1.2. Study Endpoints

1.2.1. Safety Endpoints

The safety endpoints for this study are as follows:

- adverse events (AEs) throughout the study
- vital signs assessments
- concomitant medication usage throughout the study
- physical examination findings
- clinical laboratory evaluations (hematology, clinical chemistry, and urinalysis)
- electrocardiogram (ECG) findings
- Suicidality [using the Columbia-Suicide Severity Rating Scale (C-SSRS)] and Problem Behaviors Assessment-Short form (PBA-s)

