4.3. Scoring for Rating Scales

A detailed description for all rating scales below can be found in the protocol.

The UHDRS comprises a broad assessment of features associated with HD. It is a research tool which has been developed to provide a uniform assessment of the clinical features and course of HD. The TMS component of UHDRS comprises 31 assessments from the 15 items of the UHDRS. The UHDRS-TMS is calculated as the sum of the 31 motor assessments.

The mPPT quantifies the patient's performance in physical tasks. It is a standardized 9-item test that measures the patient's performance on functional tasks. Both the speed and accuracy at which the patients complete the items are taken into account during scoring. The maximum score of the test is 36, with higher scores indicating better performance. The mPPT total score calculated as the sum of the 9 items. See [Appendix A](#) for details of the scoring method for the mPPT total score.

The TFC scale of the UHDRS assesses 5 functional domains associated with disability (occupation, finances, domestic chores, activities of daily living, and care level). Scores on each item range from 0 to either 2 or 3 (eg, Occupation: 0 = unable, 1 = marginal work only, 2 = reduced capacity for usual job, 3 = normal). The 5 items are summed to yield a TFC total score, which ranges from 0 to 13, with greater scores indicating higher functioning.

The SF-12[®] is a multipurpose short-form generic measure of health status. The 12 items in the SF-12[®] are a subset of those in the SF-36[®]; SF-12[®] includes 1 or 2 items from each of the 8 health concepts. The SF-12[®] total score is calculated as the sum of the 12 items.

The PBA-s is a brief semi-structured interview covering the most common behavioral and psychiatric manifestations of HD. The interview is not restricted to a single construct, but rather

covers several broad symptom domains relevant to HD, comprising 11 items. Each symptom is rated for both severity and for frequency on a 5-point scale. Severity and frequency scores are multiplied (after setting all values outside the range of 0-4 to missing) to produce an overall 'PBA score' for each symptom. The PBA total score is the sum of all PBA scores across the 11 symptoms.

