4.4. Handling Withdrawals and Missing Data

For all variables, only the observed data from the patients will be used in the statistical analyses, i.e., there is no plan to estimate missing data.

For the TMS component of the UHDRS, if responses to 1 assessment up to 25% of assessments are missing, the missing responses will be replaced by the average of the remaining responses within the TMS component. If responses to more than 25% of the assessments are missing, the missing responses will not be replaced and the UHDRS-TMS will be set to missing.

For mPPT, item 1 (balance tasks), item 4 (put on and remove a jacket), and item 6 (turn 360 degrees) have to be calculated before calculating the total score. For all 3 items, if any questions are missing then the missing responses will not be replaced and the item will be set to missing. After calculating items 1, 4, and 6, if responses to 1 item up to 25% of items are missing, the missing responses will be replaced by the average of the remaining responses. If responses to more than 25% of the items are missing, the missing responses will not be replaced and the total score will be set to missing.

For the TFC scale of the UHDRS, if responses to 1 item up to 25% of items are missing, the missing responses will be replaced by the average of the remaining responses within the TFC scale. If responses to more than 25% of the assessments are missing, the missing responses will not be replaced and the UHDRS-TFC will be set to missing.

For SF-12, if responses to 1 item up to 25% of items are missing, the missing responses will be replaced by the average of the remaining responses. If responses to more than 25% of the items are missing, the missing responses will not be replaced and the total score will be set to missing.

For PBA-s, the severity x frequency items need to be calculated before calculating the total score. If either the severity or frequency value is missing then the item will be equal to the nonmissing value. After calculating the items, if responses to 1 item up to 25% of items are missing, the missing responses will be replaced by the average of the remaining responses. If responses to more than 25% of the items are missing, the missing responses will not be replaced and the total score will be set to missing.

For Q-motor assessments, if either the left or right value is missing for a certain test, then the average value will be equal to the nonmissing value.

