7.8. Other Safety Assessments

Summary statistics for the C-SSRS baseline version will be presented at screening. Patients with suicidal ideation and behavior items will be summarized as categorical data using descriptive statistics.

Summary statistics for the C-SSRS last visit version will be presented at overall postbaseline. Patients with suicidal ideation and behavior items will be summarized as categorical data using descriptive statistics.

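### SAP 4.4 scores a PBA-s item with severity or frequency missing as the other rating alone, which puts a 0-4 value in place of a 0-16 product and lets the item escape the 25% missing-item rule

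*SAP*

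**What the plan says.** Protocol section 6.1.5 rates each of 11 symptoms from 0 to 4 for severity and from 0 to 4 for frequency, and states: "Severity and frequency scores are multiplied to produce an overall" score for the symptom. The frequency anchors begin "0 = symptom absent; 1 = less than once weekly". SAP section 4.3 repeats the product definition, sums the 11 products to a total, and forms the products "after setting all values outside the range of 0-4 to missing".

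SAP section 4.4 then covers an item with only one of its two ratings: "If either the severity or frequency value is missing then the item will be equal to the nonmissing value". The missing-item rule comes next, in this order: "After calculating the items, if responses to 1 item up to 25% of items are missing", they are replaced by the mean of the remaining items; above 25%, the total is set to missing.

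For the three composite mPPT items, the same section does the opposite: "if any questions are missing then the missing responses will not be replaced and the item will be set to missing".

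The total and domain scores are summarized in SAP section 6.2 as values and changes from baseline. SAP section 1.2.1 also lists PBA-s as a safety endpoint, but section 7.8 covers only the C-SSRS and no other part of section 7 summarizes PBA-s. The SAP Introduction says the SAP prevails where it differs from the protocol.

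**The concern.** A single rating and a product of two ratings are on different scales. Putting a 0-4 rating into a sum of 0-16 products amounts to assuming that the missing factor is 1, and the SAP gives no reason for that assumption. Frequency 0 means the symptom is absent, so an observed rating above 0 implies a missing factor of 1, 2, 3 or 4. The rule always takes the smallest.

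The order of steps adds a second problem. A half-missing item already has a value when the 25% rule is applied, so it is never counted as missing, and the limit on incomplete questionnaires does not reach it. SAP 4.3 supplies further cases by turning out-of-range ratings into missing ones.

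At stake is the direction of change. A half-missing item after baseline can look like behavioral improvement; one at baseline can look like later worsening. The study has no control group to expose either pattern. Because SAP section 7 has no PBA-s summary, the section 6.2 scores are the only planned PBA-s output.

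**Working it through.** The plan states no figure on this point, so there is nothing to reproduce. The check enumerates the possible ratings.

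**Inputs.** Severity 0-4, frequency 0-4 and item = product (protocol 6.1.5, SAP 4.3); 11 items (both documents); the half-missing rule and the 25% rule (SAP 4.4). Maximum item 4 x 4 = 16; maximum total 11 x 16 = 176.

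**Item error.** Let k be the observed rating and m the true value of the missing one. The SAP scores k and the true product is k x m, so error = k - km = k(1 - m).

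| Observed k | Error at m = 1 | m = 2 | m = 3 | m = 4 |
|---|---|---|---|---|
| 1 | 0 | -1 | -2 | -3 |
| 2 | 0 | -2 | -4 | -6 |
| 3 | 0 | -3 | -6 | -9 |
| 4 | 0 | -4 | -8 | -12 |

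Either rating may be the missing one, so every pair counts twice:

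- Symptom present (both ratings 1-4), 16 x 2 = 32 cases: 24 too low, 8 exact, 0 too high.
- Pairs consistent with the anchors (both 0 or both above 0), 34 cases: 24 too low, 10 exact, 0 too high.
- All pairs, 25 x 2 = 50 cases: 24 too low, 18 exact, 8 too high (by 1 to 4). The 8 need a missing rating of 0 beside an observed rating above 0, which contradicts the anchors.

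These are counts of cells, not likelihoods.

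**25% rule.** 0.25 x 11 = 2.75. Two wholly missing items (2/11 = 18%) are replaced; three (3/11 = 27%) void the total. Three to 11 half-missing items do not. For a patient with all items at 3 x 3, the true total is 11 x 9 = 99. With j items half-missing the SAP gives 9(11 - j) + 3j:

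| j | SAP total | If set to missing and counted |
|---|---|---|
| 1 | 93 | 99 |
| 2 | 87 | 99 |
| 3 | 81 | missing |
| 11 | 33 | missing |

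**Group effect.** With no missingness rate in the documents, only a yardstick is possible. If each affected patient has one half-missing item, the share of patients needed to move a visit mean by 1 point is 1/12 = 8% when those items are truly 4 x 4, 1/6 = 17% when 3 x 3, and 1/2 = 50% when 2 x 2.

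**Check of the remedy.** With one half-missing item, k above 0 and the other ten items summing to S, the bounded replacement is min(max(S/10, k), 4k). For a true 3 x 3 item (SAP error -6 throughout):

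- S = 30 gives 3, error -6
- S = 60 gives 6, error -3
- S = 90 gives 9, error 0

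It equals the SAP value whenever S is at most 10k. It can overshoot: with k = 4, m = 1 and S = 80 it gives 8, where the SAP's 4 is exact.

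**The case against.** The strongest reply is that this hardly matters. The study is single-arm and descriptive, PBA-s is one of six efficacy measures, and no test uses the total. The protocol's discontinuation criteria refer to the suicidal ideation item, not the 11-item total. The interview asks for both ratings on each symptom, and protocol sections 13.1 and 13.2 provide logical checks and a review for mandatory values, so half-missing items and out-of-range entries should be few. Similar rates at baseline and later visits would largely cancel in the mean change. The yardstick also suggests that many patients would have to be affected before a mean moved visibly. All of this stands, and it limits the weight of the point.

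A second reply is that SAP 4.4 has no uniform convention, since for Q-motor it keeps the nonmissing side. That is true, but the Q-motor score is an average of two sides, and keeping one side preserves its scale. Keeping one factor of a product does not.

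A third reply is that mean replacement is not reliably better. In one constructed profile with a true total of 50 and the 4 x 4 item half-missing, the SAP gives 50 - 16 + 4 = 38, while plain mean replacement gives 34 + 3.4 = 37.4. With the lower bound at k the replacement is 4 and the total 38, no better than the SAP. Voiding a total for three half-missing items also discards eight complete products. This stands too, and is why the remedy needs bounds and a sensitivity summary. None of it makes the present rule a valid score when it is applied.

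**Conclusion.** The concern holds. As written, the rule replaces a product by one of its factors. For a symptom that is present, the score is exact or too low, by up to 12 points on a 16-point item, and the affected items bypass the 25% limit. This follows from the item definition and the order of steps; the direction rests only on the protocol's anchors, under which a present symptom has both ratings above 0.

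The effect on visit means is unknown because no missingness rate is given, and it is probably small if the data checks work. Domain scores, which the SAP does not define, are affected only so far as they use the item. The point should be fixed before database lock, but it does not threaten the study's main conclusions.

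**What to change.** Replace the half-missing sentence in SAP 4.4 as follows:

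1. If the observed rating is 0, score the item 0.
2. Otherwise set the item to missing, as the section already does for composite mPPT items, and count it with any wholly missing items under the 25% rule, so that three or more void the total.
3. If one or two items are then replaced by the mean of the remaining items, keep the value for a half-missing item within 1 to 4 times its observed rating k.
4. Report the number of half-missing items at each visit.
5. As a sensitivity summary, report totals with those items at 1 times and at 4 times the observed rating. Each item's range is 3k wide; two items with k = 3 contribute between 6 and 24.

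The SAP should also state that step 3 returns the current value whenever the remaining items average no more than k, so the downward bias is only partly reduced.

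The cost is SAP wording and a few lines of programming. A few more totals will be missing. Replacement can overshoot when the missing rating is truly 1, and a replaced value need not be an attainable product. The totals at 1 and 4 times show this uncertainty but do not remove it.

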3.3. Efficacy Measures and Time Points

Efficacy analyses will be considered exploratory. Comparisons will generally be made to baseline, as appropriate. Efficacy endpoints include the following:

- UHDRS-TMS - will be performed at all visits during the Open-PRIDE study.
- mPPT - will be performed at baseline and at weeks 12, 26, 52, 78, 104 and 106.
- UHDRS-TFC - will be performed at baseline and at weeks 26, 52, 78, 104 and 106.
- SF-12 (acute version) - will be administered at baseline and at weeks 26, 52, 78, 104 and 106.
- PBA-s – will be performed at all visits during the Open-PRIDE study (also part of safety assessments).
- Q-motor – will be performed at baseline and at weeks 52, 78, 104 and 106.

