6.1.6.1. Digitomotography (Speeded Index Finger Tapping)

The patient will place their hand on a hand rest with their index finger positioned above a force-transducer. Recordings will start after practice runs. The patient will be instructed to finger tap as fast as possible between 2 auditory cues. The beginning of a tap is defined as a rise of the force by 0.05 N above maximal baseline level. The tap ends when it drops to 0.05 N before the maximal baseline level is reached again. The duration and variability of tap durations (TD), inter onset intervals (IOI), inter peak intervals (IPI), and inter tap intervals (ITI) are the exploratory outcome measures for speeded tapping. In addition, variability of peak tapping forces (TF) will be calculated as coefficient of variation, and the tapping frequency (Freq), ie, the number of taps between the onsets of the first and the last tap divided by the time in between, will be determined. Five trials of 10 seconds duration are performed with each hand.

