6.1.6.4. Pedomotography (Speeded Foot Tapping)

The patient will place a foot on the foot device such that the ball of the foot is positioned above a force-transducer. Recordings will start after practice runs. The patient will be instructed to tap with the foot as fast as possible between 2 auditory cues. The beginning of a tap is defined as a rise of the force by 0.05 N above maximal baseline level. The tap ends when it dropped to 0.05 N before the maximal baseline level is reached again. The duration and variability of TD, IOI, IPI, and ITI are the exploratory outcome measures for speeded tapping. In addition, variability of peak TF will be calculated as coefficient of variation, and the tapping Freq, ie, the number of taps between the onsets of the first and the last tap divided by the time in between, will be determined. Five trials of 10 seconds duration are performed with each foot.

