4.2. Specification of Baseline Values

For patients from the PRIDE-HD study, the baseline value is the last observed data prior to the first dose of study drug in this study. For patients from the ACR16C015 (OpenHART) study, the baseline value is the last observed data prior to the first dose of study drug in the Open-HART study.

ECGs at screening are performed in triplicate. If the screening value has to be used for the baseline value for patients from the PRIDE-HD study, then for the ECG variables use the mean of 3 measurements as the baseline value. For the ECG finding, use “abnormal” as the baseline value if any of the responses are abnormal, and “normal” as the baseline value if all responses are normal.

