Q-Motor assessments will be performed only in those sites that have access to the devices needed to perform the assessments and, where this is the case, only in those patients who are capable of performing the assessments. All Q-Motor assessments are based on the application of pre-calibrated and temperature-controlled force transducers and 3-dimensional position sensors with very high sensitivity and test-retest reliability across sessions and sites in a multicenter clinical study. If a certain test has a left and right value, an average value will be calculated from the test.

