6.2. Efficacy Endpoint and Analysis

The efficacy endpoints are as follows:

- UHDRS-TMS change from baseline to each visit that this is measured.
- mPPT total score change from baseline to each visit that this is measured.
- UHDRS-TFC change from baseline to each visit that this is measured.
- SF-12 total score change from baseline to each visit that this is measured.
- PBA-s total score change from baseline to each visit that this is measured.
- Q-motor assessments (digitomotography, dysdiadochomotography, manumotography and choreomotography, and pedomotography) change from baseline to each visit that this is measured.

All efficacy endpoints will be summarized for actual values and changes from baseline to each visit using descriptive statistics.

PBA-s domain scores will also be summarized for actual values and changes from baseline of this study to each visit using descriptive statistics.

No formal inferential statistics will be applied to the efficacy endpoints. Efficacy analyses will be considered exploratory.

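### Q-motor change scores can compare a two-side baseline with a one-side visit (or the reverse), because the SAP does not require the same sides at both times

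*SAP*

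**What the plan says.** Protocol 6.1.6.1 to 6.1.6.4 has every Q-motor task done on both sides. For finger tapping, "Five trials of 10 seconds duration are performed with each hand"; for foot tapping, "Five trials of 10 seconds duration are performed with each foot". Pronation/supination tapping and the grip task are also done with each hand. Under protocol 3.3, Q-motor "will be performed at baseline and at weeks 52, 78, 104 and 106".

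SAP 4.3 combines the sides: "If a certain test has a left and right value, an average value will be calculated from the test". SAP 4.4 covers the case of one missing side: "if either the left or right value is missing for a certain test, then the average value will be equal to the nonmissing value". The same section opens with the general principle that "there is no plan to estimate missing data".

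SAP 6.2 lists Q-motor change from baseline as an efficacy endpoint and states: "All efficacy endpoints will be summarized for actual values and changes from baseline to each visit using descriptive statistics". For patients from PRIDE-HD, SAP 4.2 defines baseline without reference to side: "the baseline value is the last observed data prior to the first dose of study drug in this study".

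A same-side condition does not appear in SAP 4.2, 4.3, 4.4 or 6.2, or in protocol 6.1.6 or 9.3. No by-side summary or sensitivity analysis is planned.

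**The concern.** The sides are combined at each visit before the change is taken. The set of sides behind the score can therefore differ between baseline and the visit, and the change then contains part of the patient's own left-right difference. Setting the average equal to the one observed side amounts to giving the missing side the other side's value. That sits awkwardly beside the section's opening statement on missing data.

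At stake is the precision of the Q-motor change summaries and, under a further condition, their mean. SAP 4.3 and protocol 6.1.6 describe Q-motor as highly sensitive and reliable, and the protocol says it is meant to reduce the variability of rating scales. Variation that comes only from switching sides works against that purpose. The study has no control arm in which such an effect might cancel.

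**Working it through.** The plan has no figure to reproduce. The sample size is not statistically based, and no Q-motor effect, SD, side difference or missing-side rate is given. The check applies the SAP rule to a patient with no true change, whose left value L and right value R are the same at baseline and at the visit.

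**One patient**

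| Sides at baseline | Sides at visit | Change under the SAP rule |
|---|---|---|
| both | both | 0 |
| both | R only | R − (L+R)/2 = (R−L)/2 |
| both | L only | L − (L+R)/2 = (L−R)/2 |
| L only | both | (L+R)/2 − L = (R−L)/2 |
| L only | R only | R − L |
| L only | L only | 0 |

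**With numbers.** L is set to 100; the values of R are assumptions. The baseline is two-sided and the visit one-sided.

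| R | Two-side baseline | Change, L only / R only | Size as % of baseline | Opposite single sides |
|---|---|---|---|---|
| 100 | 100 | 0 / 0 | 0 | 0 |
| 105 | 102.5 | −2.5 / +2.5 | 2.4% | 5 |
| 110 | 105 | −5 / +5 | 4.8% | 10 |
| 120 | 110 | −10 / +10 | 9.1% | 20 |
| 130 | 115 | −15 / +15 | 13.0% | 30 |

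**Group mean.** Let all patients have two-side baselines, f be the share with one side missing at the visit, d the side difference, and q the probability that the missing side is the higher-valued one. Then

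mean artefact = f × (1 − 2q) × d/2.

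With f = 10% and d = 20:
- q = 0.5: 0.10 × 0 × 10 = 0
- q = 0.75: 0.10 × (−0.5) × 10 = −0.5
- q = 1: 0.10 × (−1) × 10 = −1.0

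At the extreme q = 1, the artefact runs from 0.02 × (−1) × 5 = −0.1 (f = 2%, d = 10) to 0.20 × (−1) × 15 = −3.0 (f = 20%, d = 30).

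**Noise.** When the missing side is random (q = 0.5), the mean artefact is 0 and its variance is f × E(d²)/4. For f = 10% and d with assumed mean 10 and SD 5, E(d²) = 100 + 25 = 125. The variance is 0.10 × 125/4 = 3.125, an SD of 1.77. A simulation of 400,000 patients gave a mean of about 0 with SD 1.77. It gave a mean of −0.50 when the higher-valued side was always the missing one, as the formula predicts (0.10 × (−1) × 5).

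**Side-matched change.** If only R is present at the visit, change = R − R = 0 for every value in the table. If both sides are present at both times, the average of the two side changes equals the difference of the two averages, so the result is the same as under the SAP.

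**The case against.** The strongest case on the other side is that the problem is conditional and its consequence small. Three things must coincide: one side is missing, the observed sides differ between baseline and the visit, and the patient's sides differ in value. SAP 6.2 reports only group descriptive statistics, and the group mean is unaffected if the missing side is random. Each side has five trials, so loss of a whole side may be uncommon, although the documents do not say how trials are combined. Q-motor is one of six exploratory efficacy endpoints and is collected only at equipped sites. SAP 1.2.3 excludes patients newly enrolled after Global Amendment 02, and protocol 6.1 gives UHDRS-TMS and mPPT priority. All of this stands. It limits the importance of the point but does not remove it.

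Two stronger readings are tempting. A reader might infer that dominant and non-dominant sides differ systematically on these tasks. The protocol describes both sides of each task but says nothing about side differences, so the size has to be assumed. A reader might also infer that patients lose one side as the disease progresses, which would make the bias predictable. The only capability restriction in the documents applies to the patient, not to a side, and a patient who can no longer do a task may be missing both sides. In that case the rule does not apply.

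The fix can also be questioned. It changes the change scores but not the actual values, and it drops changes with no matching side. If a side were lost through worsening, within-side change would describe only the preserved side. The SAP rule does not recover the lost side either, and it adds the side difference on top.

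**Conclusion.** The point holds as a scoring gap. As written, the SAP allows change to be taken between different sets of sides, and an unchanged patient then shows half the left-right difference, or all of it with opposite single sides. For assumed side differences of 5%, 10% and 20% of one side, half is about 2.5%, 5% and 10% of the measure.

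At group level the rule adds noise. It biases the mean only if which side is missing depends on its value, and the documents do not support saying that this will happen. The group figures of −0.1 to −3.0 on a baseline side of 100 rest on assumed rates and differences and on the higher-valued side always being the one lost. They mark an outer range and do not estimate what this trial will show. Priority is low: Q-motor is exploratory, has no formal inference, and is not part of the primary safety objective.

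**What to change.** Amend SAP 4.4 for Q-motor as follows:
- Compute change from baseline separately for left and right.
- Average the changes over the sides present at both baseline and the visit.
- Set the change to missing if no side is present at both.
- Report the number of one-sided values at each visit.

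The tasks are done on each side, so no new data are needed, and nothing changes for patients with both sides at both times. The cost is small but not zero. A few change values are lost, and mean change may not equal the visit mean minus the baseline mean in the actual-value summaries. A table footnote can say so.
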